**Table 3-1** **Planned Cohorts, Dose Levels, Groups, and Sample Sizes for Part A**

Cohort	Vaccine	Dose Level (µg)	Group A Younger Adults $\geq 18$ to $< 65$ Years Old (n range)	Group B Older Adults $\geq 65$ Years Old (n range)	Total Cohort Sample Size
1	CV0501	12	1a (min 10; max 20)	1b (min 10; max 20)	30
2		25	2a (min 10; max 20)	2b (min 10; max 20)	30
3		50	3a (min 10; max 20)	3b (min 10; max 20)	30
4		75 or 100*	4a (min 10; max 20)	4b (min 10; max 20)	30
5		100, 150, or 200*	5a (min 10; max 20)	5b (min 10; max 20)	30

\* Depending on the reactogenicity/safety findings from groups in Cohorts 1-3, the SRT may recommend 1 of 3 prespecified dosing scenarios comprising these dose levels for groups in Cohorts 4 and 5, as described in [Section 3.1.1](#). The dose level recommendations will be made independently for Groups A (younger participants) and B (older participants).

The recruitment target will be a total of 30 participants per cohort in Cohorts 1 to 5. The 30 participants will be distributed between the younger and older age groups. A minimum of 10 participants per age group will be enrolled. A maximum of 20 participants may be enrolled in an individual age group. [CCI](#)

[REDACTED]

[REDACTED]

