## 7.5 Statistical Analysis Methodology

### 7.5.1 General Considerations

All analyses will be performed by treatment group, combining the younger and older adult participants together, unless specified otherwise. For categorical variables, frequencies and percentages will be presented. Continuous variables will be summarized using descriptive statistics (number of participants, mean, median, standard deviation, minimum, and maximum).

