### 13.3 Appendix 3: Bayesian Logistic Regression Model

A Bayesian logistic regression model will be used to determine posterior probabilities of unacceptable reactogenicity (Grade 3 solicited AEs) at the current or next dose level in Part A, as described below:

$$\text{logit}(p(d)) = (\alpha + \beta_1 * \log(d/d^*)) + \beta_2 (\text{indicator of OA})$$

where

- $p(d)$  represents the probability of having a Grade 3 event at dose  $d$ ,
- $\text{logit}(p) = \ln(p/(1-p))$ ,
- $d^* = 50 \mu\text{g}$  is the reference dose,
- $\alpha$  is an intercept parameter, reflecting the expected logit value at the  $50 \mu\text{g}$  reference dose level,
- $\beta_1$  is a dose effect,
- $\beta_2$  is an age group effect.

The prior for  $\alpha$  and  $\ln(\beta_1)$  is a mixture of 2 bivariate normal distributions:

1. 80% weight for  $\alpha \approx \text{normal}(\text{mean}=-0.8473, \text{var}=1)$  and  $\ln(\beta_1) \approx \text{normal}(\text{mean}=-0.0556, \text{var}=1)$ , reflecting a rate of 30% at  $50 \mu\text{g}$ , and 10% at  $12 \mu\text{g}$ .
2. 20% weight for  $\alpha \approx \text{normal}(\text{mean}=-0.4055, \text{var}=1)$  and  $\ln(\beta_1) \approx \text{normal}(\text{mean}=0.10612, \text{var}=1)$ , reflecting an intolerable dose (ie, a rate of 40% at  $50 \mu\text{g}$  and 12% at  $12 \mu\text{g}$ ).

The prior  $\beta_2$  is half normal ( $\text{mean}=0$ ,  $\text{variance}=0.25$ ,  $\beta_2 < 0$  to reflect lower reactogenicity in older age group [OA]).

The covariance between priors is assumed to be zero.

A greater than 50% posterior probability that the rate at a current or next dose is greater than 30% will inform the SRT in their decision to continue at the current or next dose. This will be applied by each dose and age group.

Hypothetical scenarios for determining posterior probabilities based on combined younger age group and older age group data are presented in [Table 13-2](#).

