3.1. Overall Study Design and Plan

This open-label, dose escalation first-time-in human (FtiH) Phase 1 study will evaluate the safety (including reactogenicity) and immunogenicity of a single booster dose of CV0501 vaccine in adults who have previously received at least 2 doses of an mRNA COVID-19 vaccine. Approximately 180 participants will be enrolled. The study will comprise two parts (Part A and Part B).

Part A: Participants in Cohorts 1 to 5 will be enrolled in a staggered manner to 1 of 5 cohorts with planned dose escalation of CV0501 from 12 µg up to 200 µg. Each cohort of Part A will evaluate a single dose level of CV0501 vaccine and will include 2 age groups (younger adults, ≥ 18 to < 65 years old, and older adults, ≥ 65 years old), as indicated in Table 3-1. The dose levels for the groups in Cohorts 1-3 are fixed. The dose levels for the Cohorts 4 and 5 will be as recommended by the SRT, based on their review of all available safety data and dosing scenarios.

Part B: Designed to comprise 2 single age group cohorts (≥ 18 to < 65 years old), will start based on the first interim analysis of safety and immunogenicity, provided that the SRT assesses the 12 μ g dose to be immunogenic and safe. The SRT may recommend dropping Cohorts 6 and 7 (Groups 6a and 7a) based on immunogenicity data from the groups that received the 12 μ g dose level. If the SRT determines that enrollment in Cohorts 6 and 7 may proceed, enrollment may proceed in parallel according to Table 3-2.

[figure not shown]
[figure not shown]
Table 3 1 Study Cohorts, Groups, and Study Vaccine Administration (Part A)

Cohort	Vaccine	Dose Level	Group A Younger Adults ≥ 18 to < 65 Years of Age (n range)	Group B Older Adults ≥ 65 Years of Age (n range)	Total Cohort Sample Size
1	CV0501	12 μ g	1a (min 10; max 20)	1b (min 10; max 20)	30
2		25 μ g	2a (min 10; max 20)	2b (min 10; max 20)	30
3		50 μ g	3a (min 10; max 20)	3b (min 10; max 20)	30
4		75 or 100* μ g	4a (min 10; max 20)	4b (min 10; max 20)	30
5		100,150, or 200* μ g	5a (min 10; max 20)	5b (min 10; max 20)	30

*Depending on the reactogenicity/safety findings from groups in Cohorts 1-3, the SRT may recommend 1 of 3 prespecified dosing scenarios comprising these dose levels for groups in Cohorts 4 and 5, as described in Section 3.1.1 of protocol. The dose level recommendations will be made independently for Groups A (younger participants) and B (older participants).

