4.1. Sample Size

The sample size is based on clinical considerations to inform dose regimen decisions for continued clinical development.

Approximately 180 participants will be enrolled in this Phase 1 study, 5 dose-level cohorts (Cohorts 1 to 5) each comprising 2 age groups. Cohorts 6 and 7 will comprise 1 age group (younger adults). With 30 participants in each cohort, there is a 78.5% probability to observe at least 1 AE if the incidence rate is 5% and a 95.8% probability to observe at least 1 AE if the incidence rate is 10%. With 30 participants in each cohort, a 10% unevaluable rate for immunogenicity results, and a standard deviation of 0.45 for log10-transformed increase from day 1, the ratio of the upper limit of a 2-sided 95% CI and the point estimate of geometric mean increase (GMI) is 1.5. The sample size in Cohorts 6 and 7 is based on clinical feasibility rather than on statistical rationale. With 15 participants in each cohort, there is a 79.4% probability to observe at least one AE if the true incidence rate is 10%.

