The GMT at each postvaccination time point, the GMI from baseline, and the 95% CIs in all cohorts will be analyzed using an ANCOVA model on log10 transformed titers with dose group and age group as fixed in the model and prior Covid-19 infection and prevaccination baseline value as covariates.

[figure not shown]
8.2.2. Seroresponse rate 28 days after the booster dose (day 29), based on neutralizing Ab titers against pseudoviruses bearing S protein from SARS-CoV-2 WT, Omicron BA.1, BA.2 and BA.5 variants at each collection timepoint, with seroresponse defined as postboost titers $\geq 4 \times$ preboost titers.

Proportion of participants with neutralizing seroresponse of serum SARS-CoV-2 WT, Omicron BA.1, BA.2 and BA.5 variants specific Ab from baseline at day 29 by dose group and prior Covid-19 infection will be tabulated with 2-sided 95% Clopper Pearson CIs. The same summaries will be generated for seroresponse rate 14 days after booster dose (Day 15) as supportive analyses.

[figure not shown]
CCI

CCI

CCI

Approved

CCI

9 Safety Analysis

Safety, tolerability, and reactogenicity will be assessed by clinical review of all relevant parameters including solicited and unsolicited AEs, SAEs, AESIs, MAAEs, AEs leading to withdrawal from study participation, safety laboratory test results, vital signs, and physical examination findings.

All safety analyses will be based on Safety Set. All safety analyses will be provided by dose group and age group unless otherwise specified.

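### Seroresponse is tabulated by dose with ages pooled, although the 3 and 6 µg groups hold no older adults, so rates read across doses mix dose with age

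*SAP*

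**What the plan says.** **Who is in each dose group.** Part B (3 and 6 µg, 15 each) is "Designed to comprise 2 single age group cohorts", both of adults aged 18 to under 65 (SAP 3.1; also SAP 4.1). Part A has 30 per cohort, and for the age split Protocol 3.1 says: "A minimum of 10 participants per age group will be enrolled. A maximum of 20 participants may be enrolled in an individual age group". For Cohorts 4 and 5 the dose is chosen independently for younger and older adults from three scenarios (Protocol 3.1.1, Table 3-2).

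**How results are grouped.**
- Protocol 7.5.1 sets the default: "All analyses will be performed by treatment group, combining the younger and older adult participants together, unless specified otherwise".
- Seroresponse (SAP 8.2.2): proportions "by dose group and prior Covid-19 infection will be tabulated with 2-sided 95% Clopper Pearson CIs". The supportive Day 15 summary follows the same layout. Age is not named.
- GMT and GMI (SAP 8.2.1): an ANCOVA with "dose group and age group as fixed in the model", plus GMI by age group and GMT bar charts that include age group.
- Safety: SAP 9 sets dose and age group as the default. SAP 9.1 sets dose group alone for AEs. SAP 9.1.4 gives any local and any systemic solicited AE by age and dose. SAP 9.1.5 gives unsolicited AEs by age and dose, and SAP 8.1.2 does so for MAAEs and SAEs. SAP 8.1.1 and the maximum-severity summary in 9.1.4 name dose group only.

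**What the plan expects of age.** The escalation model constrains its age effect to be negative, "to reflect lower reactogenicity in older age group" (Protocol 13.3).

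**The concern.** A reader of the seroresponse table will look along the dose columns. The 3 and 6 µg columns describe adults under 65. The 12, 25 and 50 µg columns describe a mixture whose older share is not fixed. If response differs by age, columns differ even where dose has no effect.

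The problem is not confined to Part B. Two fixed-dose cohorts can differ in age split (10:20 against 20:10). In Cohorts 4 and 5, if older adults followed scenario 1 (75 then 100 µg) and younger adults scenario 3 (100 then 200 µg), the 75 µg column would be all older and the 200 µg column all younger.

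The study is meant to guide the Phase 2 dose, and Part B asks whether doses below 12 µg deserve further work. There is no hypothesis testing, so these side-by-side estimates are the evidence. Seroresponse comes from the same titres as GMT and GMI but has neither their age adjustment nor an age-specific display.

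**Working it through.** **1. The plan's own figures (Protocol 7.2, SAP 4.1).**
- At least one AE: 1 − 0.95^30 = 78.5%; 1 − 0.90^30 = 95.8%; 1 − 0.90^15 = 79.4%.
- GMI precision, 27 evaluable of 30, SD 0.45: 10^(t × 0.45/√27) = 1.507, stated as 1.5.

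All reproduce. They treat each cohort as one sample and do not address age mix.

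**2. Older share.** In the fixed-dose cohorts w = 10/30 to 20/30, that is 33% to 67%. In Cohorts 6 and 7, w = 0.

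**3. Gap created by age mix alone.** Let y and o be the younger and older rates, the same at every dose. A pooled Part A column shows (1 − w)y + w·o and a Part B column shows y. The difference is w(y − o).

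**4. Seroresponse.** The documents give no age-specific rates, so y − o is an assumption. The table shows the absolute size; the sign follows that of y − o.

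| Assumed age difference (points) | Gap at w = 1/3 | Gap at w = 2/3 |
|---|---|---|
| 5 | 1.7 | 3.3 |
| 10 | 3.3 | 6.7 |
| 20 | 6.7 | 13.3 |
| 30 | 10.0 | 20.0 |

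**5. Grade 3 solicited events (maximum-severity summary).** Here the protocol supplies an age effect: a half-normal prior on the logit scale, negative, variance 0.25. I read 0.25 as the variance of the parent normal (SD 0.5). The mean size is 0.5 × √(2/π) = 0.40 and the 95th percentile is 1.96 × 0.5 = 0.98. The main prior component puts the rate at 30% at 50 µg and 10% at 12 µg, so both are used as the younger rate.

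| Younger rate | Age effect (logit) | Older rate | Pooled Part A rate | Gap (points) |
|---|---|---|---|---|
| 30% | −0.40 (mean) | 22.3% | 24.9–27.4% | 2.6–5.1 |
| 30% | −0.98 (95th percentile) | 13.9% | 19.2–24.6% | 5.4–10.8 |
| 10% | −0.40 (mean) | 6.9% | 8.0–9.0% | 1.0–2.0 |

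**6. After an age split.** Within adults under 65, w = 0 in every column and the gap is 0. The cost is precision. Clopper-Pearson 95% limits at an assumed 80% response:
- 24/30 (pooled cohort): 61.4–92.3%
- 16/20: 56.3–94.3%
- 8/10: 44.4–97.5%
- 12/15 (a Part B cohort): 51.9–95.7%

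**The case against.** The case against acting is substantial, and parts of it stand.

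- **Safety is largely covered.** A reader might infer that reactogenicity as a whole is confounded with age. The documents do not support that: the SAP 9 default and the age splits in 8.1.2, 9.1.4 and 9.1.5 already let 12 µg adults under 65 be set beside Groups 6a and 7a. What remains is 8.1.1, maximum severity and the clash between the 9 and 9.1 defaults.
- **The ANCOVA is not at fault.** A reader might infer that adjusted means at 3 and 6 µg are invalid because they average over an age group that never received those doses. The stated model has no dose-by-age interaction, so the age weighting shifts every adjusted log mean equally and leaves dose ratios unchanged. Additivity cannot be checked at 3 and 6 µg, which justifies at most a sensitivity analysis.
- **The direction is not known.** A reader might infer that low doses will look more immunogenic than they are. Seroresponse is a fourfold rise over baseline. Protocol 1.1 reports that waning is most pronounced in older adults, so lower baselines could make a fourfold rise easier for them and reverse the sign.
- **No Part B against 12 µg test is planned.** Protocol 3.3.4 gives the aim as platform optimization for multivalent vaccines, and SAP 12 says it is unsure whether these cohorts will be enrolled. With 15 participants, a 7 to 13 point shift lies well inside the interval for 12/15. This limits the consequence, but wide intervals do not remove a systematic difference between columns.
- **Table shells may add age splits.** SAP 4 leaves details of the safety displays to shells that are not among the documents. The SAP text should still specify the split for a secondary endpoint.

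**Conclusion.** The point holds for seroresponse. As written, the SAP gives no seroresponse result in which dose can be read free of age. With no dose effect, the spurious gap is 1.7 to 20 points for assumed age differences of 5 to 30 points, in an unknown direction. This assumes that the enrolment limits are met and that the analysed participants keep the enrolled age mix. The one-third to two-thirds range applies to the fixed doses (12, 25 and 50 µg); a Cohort 4 or 5 dose level could lie anywhere from all younger to all older.

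For safety the point is narrow: the 8.1.1 percentages, the maximum-severity summary and the conflicting defaults. Maximum severity matters most, because it shows Grade 3 events, the outcome behind the 30% maximum tolerable rate. The prior-based gaps of 1.0 to 10.8 points apply to that summary. They do not apply to 8.1.1, which counts participants with any such event. The upper end needs both a 30% younger rate and an age effect at the prior's 95th percentile.

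This should be corrected before the outputs are finalized. It does not undermine the primary objective or the GMT and GMI analyses.

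**What to change.** 1. In SAP 8.2.2, tabulate seroresponse at Day 29 and Day 15 by dose and age group with Clopper-Pearson intervals. Show Groups 6a and 7a beside Group 1a and the other under-65 groups. A dose-by-age table is enough; crossing it with prior infection as well would leave very small cells.
2. Give the 8.1.1 percentages and the maximum-severity summary of solicited AEs by dose and age group.
3. Reconcile the defaults in SAP 9 and 9.1 so that one grouping rule applies to AEs.
4. Keep the pooled tables alongside if wanted, with the age split shown per dose column.
5. Optional: rerun the GMT and GMI ANCOVA in adults under 65 only, as a sensitivity analysis.

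The cost is a few table columns on data already collected, and wider age-specific intervals: at an assumed 80%, 16/20 spans 38.0 points (94.3 − 56.3) against 30.9 (92.3 − 61.4) for 24/30.

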9.1 Adverse Events

An AE is any untoward medical occurrence in a participant enrolled into this study regardless of its causal relationship to the IP. This definition includes exacerbations of pre-existing conditions. Stable pre-existing conditions which do not change in nature or severity during the study are not considered AEs; however, these should be reported as part of the medical history at screening.

SOC will be displayed in alphabetical order. PT will also be displayed alphabetically within SOC. Percentages will be based upon the number of participants in the Safety Set within each dose group.

Incomplete AE onset date/time and end date will be imputed following the rules below.

Missing Start Dates

If day is missing and month and year are available:

- UK-MMM-YYYY: Assume 01-MMM-YYYY (first day of the month), but if month and year are the same as the first study vaccination month and year, then assume the date of first vaccination.

If day and month are missing and year is available:

- UK-UKN-YYYY: Assume 01-JAN-YYYY (first day of the year), but if year is the same as the first study vaccination year, then assume the date of first study vaccination.

If day, month and year (date) are missing:

- UK-UKN-UNKN: Assume date of first study vaccination.

Missing Stop Dates

If day missing and month and year are available:

- UK-MMM-YYYY: Assume the last day of the month

If day and month are missing and year is available:

- UK-UKN-YYYY: Assume 31-DEC-YYYY

If day, month and year (date) are missing:

- UK-UKN-UNKN: Do not impute and assume ongoing

All adverse events will be classified by SOC and PT according to the MedDRA.

Unless otherwise specified, AEs will be summarized by dose group based on Safety Set. A listing of AEs will be provided by age group, dose group and participant number.

All events from screening until vaccination will be considered as medical history.

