## 5.8 Prior, Concomitant, and Rescue Therapies

### 5.8.1 Prior and Concomitant Therapy

Use of all prior and concomitant medications and vaccinations within 6 months of screening will be recorded in the participant's eCRF.

All prior COVID-19 vaccines received (including those received more than 6 months before screening) and all COVID-19 vaccines received during the study will be recorded.

The minimum requirement is that drug name and the dates of administration are to be recorded. This will include all prescription drugs and vaccinations. In addition, any herbal products, vitamins, minerals, and over-the-counter medications taken within 2 weeks of study vaccination should also be recorded in the participant's eCRF. Any changes in concomitant medications also will be recorded in the participant's eCRF throughout the study.

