### **6.1.1.2 Eliciting and Documenting Adverse Events**

Adverse events will be reported throughout the study. Nonserious AEs will be reported from the time of the administration of IP until 28 days after the administration of IP; SAEs will be reported from the time the participant signs the ICF until exit from the study.

If the investigator learns of any SAE, including a death, at any time after a participant has been discharged from the study, and he/she considers the event to be reasonably related to the IP, the investigator must notify PPD Pharmacovigilance within 24 hours of learning of the event ([Section 6.1.1.3.1](#)).

At every study visit, participants will be asked a standard nonleading question to elicit any medically related changes in their well-being.

In addition to participant observations, AEs identified from any study data (eg, laboratory values, physical examination findings) or identified from review of other documents (eg, participant eDiaries) that are relevant to participant safety will be documented on the AE page in the eCRF.

As described in [Section 6.1.1.1.1](#), participant eDiaries will be used to collect solicited AEs.

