7.1.2. Concomitant Medications

Concomitant medications are defined as any medications and vaccine (other than study vaccines) taken after the study vaccine is administered and:

- Within 6 months of Screening or
- Were taken first prior to the dosing and on-going after study vaccine dose up to 6 months or
- Within 2 weeks of study vaccination for herbal products, vitamins, minerals, and over-the-counter medications.

Concomitant medications will be listed and summarized in a similar manner to that of prior medications.

For the purpose of inclusion in prior and concomitant medications tables, incomplete start and stop dates will be imputed according to the below rules (where UK, UKN, and UNKN indicate unknown or missing day, month, and year, respectively):

Missing Start Dates

If day is missing and month and year are available:

- UK-MMM-YYYY: Assume 01-MMM-YYYY (first day of the month), but if month and year are the same as the first study vaccination month and year, then assume the date of first vaccination.

If day and month are missing and year is available:

- UK-UKN-YYYY: Assume 01-JAN-YYYY (first day of the year), but if year is the same as the first study vaccination year, then assume the date of first study vaccination.

If day, month and year (date) are missing:

- UK-UKN-UNKN: Assume date of first study vaccination.

Missing Stop Dates

If day missing and month and year are available:

- UK-MMM-YYYY: Assume the last day of the month

If day and month are missing and year is available:

- UK-UKN-YYYY: Assume 31-DEC-YYYY

If day, month and year (date) are missing:

- UK-UKN-UNKN: Do not impute and assume ongoing

(Note - In case of single dose vaccine or treatment, start date may be same as that of end date.)

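### The missing-start-date rules in SAP 9.1 and 7.1.2 never consult the stop date, so a record that ended before vaccination can be given a Day 1 start after its own end

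*SAP*

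**What the plan says.** SAP 9.1 (adverse events) has three rules for an incomplete start date. Each can return the vaccination date:

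- Day missing: the vaccination date if the known month and year match those of vaccination. SAP 7.1.2 words the same rule as "but if month and year are the same as the first study vaccination month and year, then assume the date of first vaccination".
- Day and month missing: "if year is the same as the first study vaccination year, then assume the date of first study vaccination".
- Nothing known: "UK-UKN-UNKN: Assume date of first study vaccination".

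SAP 7.1.2 repeats the three rules for medications and vaccines and says what they are for: "For the purpose of inclusion in prior and concomitant medications tables, incomplete start and stop dates will be imputed according to the below rules".

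The stop-date rules in both sections deal only with stops that are themselves incomplete. The last of them reads "UK-UKN-UNKN: Do not impute and assume ongoing". A complete stop date is left alone and is never compared with the start. A note in 7.1.2 allows start and stop to coincide for a single-dose product, but it does not require a start to be on or before its stop.

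Two further statements bear on adverse events. SAP 9.1 ends its general rules with "All events from screening until vaccination will be considered as medical history". Protocol 6.1.1.2 says "SAEs will be reported from the time the participant signs the ICF until exit from the study", and SAP 9.1.7 likewise says SAEs are summarized and listed from consent, although the same sentence closes with day 1-180.

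**The concern.** Setting an uncertain onset to the vaccination date is a usual conservative choice for safety data, because it keeps a doubtful event inside the observation window. It is conservative only while a post-vaccination onset is possible. If the recorded stop is before vaccination, the data already exclude such an onset, and the rule overrides what is known.

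Records of this kind can arise by design. SAEs are collected from consent, over a screening period of about 14 days. Medications go back much further: "Use of all prior and concomitant medications and vaccinations within 6 months of screening will be recorded" (Protocol 5.8.1). Partial start dates are more plausible in that older history.

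At stake are the correct split between prior and concomitant medications, and a dataset free of impossible date sequences. To a much smaller extent, so is the SAE percentage, which is a primary endpoint.

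**Working it through.** The plan gives no figure on this point, so there is none to reproduce. The check applies the rules literally to test records.

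**Inputs.** Start and stop rules: SAP 9.1 and 7.1.2. Study day on or after injection: assessment date - injection date + 1 (SAP 4). The vaccination date of 15-SEP-2022 is an assumption, since the documents give no participant dates.

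| Record | Recorded start | Recorded stop | Start under the SAP rules | Imputed start minus stop |
|---|---|---|---|---|
| A. SAE after consent | UK-SEP-2022 | 08-SEP-2022 | 15-SEP-2022 | 15 - 8 = +7 days |
| B. Medication | UK-UKN-2022 | 20-APR-2022 | 15-SEP-2022 | 10 + 31 + 30 + 31 + 31 + 15 = +148 days |
| C. Medication | wholly unknown | 20-APR-2022 | 15-SEP-2022 | +148 days |
| D. Medication | UK-UKN-2022 | UK-AUG-2022, imputed to 31-AUG-2022 | 15-SEP-2022 | +15 days |
| E. Control: earlier month | UK-AUG-2022 | 08-SEP-2022 | 01-AUG-2022 | in order |
| F. Control: earlier year | UK-UKN-2021 | 20-APR-2022 | 01-JAN-2021 | in order |
| G. Control: stop after vaccination | UK-SEP-2022 | 25-SEP-2022 | 15-SEP-2022 | in order |

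A to D start after they end. In D, the start rule contradicts the SAP's own imputed stop. E to G behave properly. The fault therefore needs two things together: a start that is wholly unknown or whose known part matches vaccination, and a stop known to be before vaccination.

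**Effect on the tables.** The imputed start is study day 0 + 1 = 1. SAP 9.1.7 selects SAEs by onset within day 1-28 and day 1-180, so record A qualifies for both if the imputed onset is used. SAP 7.1.2 defines concomitant medication as taken after the study vaccine and uses imputed dates for table inclusion, so B to D can be counted as concomitant if the imputed start is what is tested.

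**Weight of a single misdated SAE.** 1/30 = 3.3 percentage points in a planned cohort of 30, and 1/15 = 6.7 points in a Part B cohort of 15. This is the weight of one hypothetical record, not an expected bias.

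**With a stop-date condition.** A starts on 01-SEP-2022, B and D on 01-JAN-2022, and C on its stop date, 20-APR-2022. All four are in order and pre-vaccination. E to G are unchanged.

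**The case against.** A reader might infer that screening-period SAEs will be counted in the primary SAE percentage. The documents do not support that. An SAE recorded as ending on 08-SEP, before a 15-SEP vaccination, is on its recorded data an event between screening and vaccination, and SAP 9.1 makes that medical history. SAP 6.3.1 has a medical-history category for conditions already ended. The endpoint counts SAEs from study vaccination (Protocol Table 2-1; SAP 2.1 and 8.1.2). Applied before imputation, these provisions keep the event out.

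The scenario is also narrow. It needs an SAE during about 14 days of screening that resolved before Day 1, with its stop known but its onset day unknown, in someone who passed the Day 1 eligibility reassessment and was vaccinated. SAEs are reported within 24 hours of site awareness, time of onset is a collected item, and data cleaning should query inconsistent dates.

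For medications, a programmer who tests the stop date would see that a course ending in April was not taken after a September vaccination. The tables concerned are descriptive.

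Most of this stands, and it limits the size of the point. It does not remove it. The SAP does not say whether the medical-history rule is applied before or after imputation, or on which date, and the from-consent wording in 9.1.7 blurs it further. Nor does 7.1.2 say that the stop date decides concomitant status. Even with correct classification, the record would still carry a start later than its stop.

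**Conclusion.** The point holds as a minor correction. The start-date rules in SAP 9.1 and 7.1.2 lack a stop-date condition and, read literally, give impossible sequences for records known to have ended before vaccination. A past medication can then be counted as concomitant. A screening-period SAE can fall in the day 1-180 window only if the medical-history rule is not applied first.

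The main reach is the medication tables. Few or no SAEs are expected, and no main conclusion is expected to change. The documents give no count of partial dates, so the number of affected records cannot be stated. The day counts of 7, 148 and 15 depend on the assumed dates; the reversal itself does not.

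Two wider inferences are not supported:

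- That every year-only medication start in the vaccination year is misplaced. Where the stop is missing or on or after vaccination, the vaccination-date default does no harm. How often the year matches also depends on the calendar. With starts spread evenly over the 196 days before vaccination (14 of screening plus 182 for 6 months), it is 100% for vaccinations in August-December 2022 but 23% for January-March 2023.
- That an earlier single-dose vaccine dated only to the vaccination year shows the same fault. It has no stop known to precede vaccination. A year-only stop would be imputed to 31-DEC-2022, so the start does not follow the stop, and a stop-date condition would not alter the record.

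**What to change.** Add to both SAP 9.1 and SAP 7.1.2:

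*Use the vaccination date only if the stop date is missing or could be on or after vaccination. If the stop date, or its known part, is before vaccination, impute the start as the earliest date consistent with the known parts (or as the stop date if the start is wholly unknown), never after the stop, and class the record as pre-vaccination.*

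Add to SAP 9.1:

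*The rule that events between screening and vaccination are medical history is applied to recorded dates, before any imputation.*

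The from-consent wording in SAP 9.1.7 should be read or edited to agree with this. All other incomplete starts keep the present default. The cost is a few sentences in the SAP and a few lines of programming, with no change to data collection or to any endpoint.
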